**Exclusion Criteria**

1. History of heart attack or stroke within past 6 months
2. Untreated hypertension, hyperlipidemia, or diabetes, unless permission is provided by their health care provider.
3. Health problems which preclude ability to walk for PA
4. Report a heart condition, chest pain during periods of activity or rest, or loss of consciousness on the Physical Activity Readiness Questionnaire (PAR-Q; items 1-4).
5. Report a past diagnosis of or receiving treatment for a DSM-IV-TR eating disorder (anorexia nervosa or bulimia nervosa).
6. Currently pregnant, pregnant within the past 6 months, or planning to become pregnant within the next 6 months.
7. Hospitalization for depression or other psychiatric disorder within the past 12 months. History of psychotic disorder or bipolar disorder.
8. Plans for major surgery (e.g., breast reconstruction) during the study time

---

frame

9. Currently participating in a weight loss, nutrition or physical activity study or program or other study that would interfere with this study.
10. Currently using prescription weight loss medications

Number Of Subjects	72
Study Duration	Each subject's participation will last 4 months.
Study Phases	
Screening	(1) Screening : screening for eligibility and obtaining consent and (2) Baseline assessment
Study Treatment	(3) Intervention : study intervention/experimental treatment.
Follow-Up	(4) Follow-up assessment will occur at 6 weeks and 3 months
Efficacy Evaluations	NA
Pharmacokinetic Evaluations	NA
Safety Evaluations	All medical events and safety data will be assessed at assessment points or when interim events are reported by participants using a standard form used in our ongoing NIH funded trials.
Statistical And Analytic Plan	
The primary objective is to evaluate the feasibility and acceptability of a digital intervention components to increase PA and improve nutrition behaviors among YACS (n=80) at 3 months. Our primary feasibility measures are participation, accrual, and retention rates.
 
The secondary outcome analysis will use mixed effects models to test for differences in MVPA and HEI by intervention components across time (baseline, 6 weeks, and 3 months). Effects will be modeled as component x time interactions with the 3-month outcome as the primary endpoint.

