## **3. STUDY PROCEDURES**

### **Data Collection**

All study participants will complete objective weight measurements, two dietary recalls, and self-administered online surveys at baseline and 3 months (post-intervention). At 6 weeks, only psychosocial measures and medical events will be collected via online survey and telephone. Participants will receive \$25 for completing the 3-month assessments. Online surveys will include measures of theoretical mediators, other psychosocial constructs, and process measures. We will send emails and texts prompting participants to complete assessments, with follow-up emails and phone calls to non-respondents, as necessary. Measures and timing are described below.

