## Measures

### ***Behavioral Measures (collected at baseline and 3 months)***

Device-measured physical activity will be assessed at baseline and 3 months using the study provided activity tracker. Participants will be instructed to wear the device at all times for a full week; monitoring for at least 600 min/day for at least 4 days in the week (including at least one weekday and one weekend day) is considered adequate for analysis. Data are transmitted to Fitbit each time the participant syncs their tracker with the Fitbit app on their phone. Weekly minutes of moderate-to-vigorous activity (termed “active minutes” in Fitbit) and steps per day will be computed from the participant’s Fitbit data and averaged over a minimum of 4 out of a 7-day period.

Self-reported physical activity will be assessed using the Paffenbarger Activity Scale (PAQ), which assesses leisure-time activity. The PAQ provides an estimate of minutes per week of moderate-to-vigorous intensity, and calories/week of light (5 kcal/min), medium (7.5 kcal/min), and high (10 kcal/min) intensity activities. PAQ changes have been predictive of weight change.

Dietary Intake: Changes in dietary intake will be assessed using the NCI’s 24-hour Recall (ASA-24) by trained administrators. Participants will complete two self-reported recalls; one weekday and one weekend day. The 24 recall is a validated method of measuring diet. Using two recalls permits adjustment of estimates for intraindividual variation and is superior to administering one recall. We will examine change in overall energy intake and saturated fat intake, as well as change in fruit and vegetable consumption, fiber consumption, and change in the Healthy Eating Index score.

Healthy Eating Index: The HEI-2020^78 consists of 13 component scores, including: total fruit, whole fruit, total protein foods, total vegetables, greens and beans, whole grains, dairy, seafood and plant proteins, fatty acids, sodium, refined grains, added sugars, and saturated fats. The summation of the 13 component scores ranges from 0 to 100, with higher scores indicating closer compliance with the 2020 DGA.

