## 4. STATISTICAL CONSIDERATIONS

### Sample Size and Power

The sample size is based on feasibility. Our primary feasibility measures are participation, accrual, and retention rates. Anticipated participation and retention rates are based on pilot feasibility studies among YACS and our previous work with this population. With an estimated participation rate of 85% (consistent with CO-I's experience, LCCC 1707), we anticipate it will be feasible to recruit 80 YACS within 6 months. We will test the null hypothesis that the proportion recruited is 50% or lower versus the alternative that it is 65% or greater using a one-tailed test at an alpha level of 0.05 with 95% power, which would support that the study is feasible.

We plan to accrue no more than 100 participants looking to have at least 80 evaluable participants, for 5 participants in each of the 16 groups. We expect accrual to take a total of 10 months at a rate of approximately 10 participants per month. We anticipate accruing 80 participants within 10 months, or 12-15 participants per month. A sample size of 80 achieves 99% power to detect a difference between a null hypothesis mean accrual rate of 12 participants/month and an alternative hypothesis mean of 15 participants/month with a significance level of 0.05 using a one-sided one-sample Poisson test.

For retention, we will test the null hypothesis that the retention is 70% or below versus the alternative that the retention is 90% or greater using a one-tailed test at a 0.05 alpha level. With 80 participants we would reject the null hypothesis that the retention is 70% if at least 62 participants are retained with 90% power, which would support that the study is feasible. With 80 participants we would reject the null hypothesis that the retention is 70% if at least 66 participants are retained with 97% power, which would support that the study is feasible.

All three endpoints must meet the proscribed criteria in order for the study to have successfully demonstrated feasibility.

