Using maximum likelihood methods, we will use mixed model analyses with repeated measures to estimate changes in MVPA and HEI (and other secondary measures; Objectives 2.1.5-2.1.7) at 3 months and to test for statistical differences across conditions in changes over time, adjusting for age, cancer type, and time since diagnosis. Models will include random intercept, time, component, and component\*time variables. A proper error covariance structure will be chosen based on model fit indicated by model likelihood, Akaike Information Criterion and Bayesian information Criterion.

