- C) Advertisements. We will place sponsored posts on social media, ads on relevant internet sites, and use email listservs. We will produce flyers, posters, brochures, and presentations to advertise the study at community events and cancer conferences dedicated to young adults (e.g., CancerCon, AYA Global Congress). We will work with the UNC AYA Oncology clinical staff with whom we have established relationships (i.e., Co-Investigator [name], Medical Director, UNC AYA Oncology; [name]) to advertise the study and recruit potentially interested individuals.

All recruitment efforts will direct participants to a study website with a more detailed description of the research study and FAQs about participating in research. Interested individuals will click through to a REDCap web screening survey to determine initial eligibility. Those who are preliminarily eligible will be contacted by trained study staff and will undergo additional phone screening. Following an approach we have used in the past, eligible and interested individuals will receive an email directing them to a unique REDCap link to an online informed consent. After providing consent, participants will be instructed on procedures for 1) completing one weekday and one weekend self-reported 24-hour dietary recall, 2) completing baseline online questionnaires, and 3) completing their baseline weight measurement. The Fitbit activity tracker will be mailed to the participant. After completion of baseline assessments, the participant will be randomized to one level of each of the 4 factors, or one of the 16 conditions (Table 1). The participant will be scheduled for a one-on-one telephone/videochat session during which they will be informed of condition assignments, assisted with downloading of the study smartphone app, and questions about getting started will be answered.

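### Component effects on MVPA and HEI are planned as differences in change with baseline means left free; adjusting for the baseline value would generally be more precise, by an amount the documents do not fix

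*Combined protocol and SAP*

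**What the plan says.** Section 4, Statistical Analysis, plans a maximum likelihood repeated-measures model for MVPA, HEI and other secondary measures. Its purpose is "to test for statistical differences across conditions in changes over time, adjusting for age, cancer type, and time since diagnosis". The terms are listed: "Models will include random intercept, time, component, and component\*time variables". The covariance structure is to be picked by fit criteria. The Protocol Synopsis, Statistical And Analytic Plan, agrees on the target: "Effects will be modeled as component x time interactions with the 3-month outcome as the primary endpoint". Neither place names the baseline value of the outcome as a covariate or holds the component levels to a common baseline mean.

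Three other places matter:

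- Section 3, Measures, schedules MVPA and HEI at two times: "Behavioral Measures (collected at baseline and 3 months". Data Collection confirms it: "At 6 weeks, only psychosocial measures and medical events will be collected via online survey and telephone". The synopsis does list 6 weeks among the MVPA and HEI time points, which conflicts with Section 3.
- Recruitment puts randomisation after baseline: "After completion of baseline assessments, the participant will be randomized to one level of each of the 4 factors".
- Sample Size and Power plans "looking to have at least 80 evaluable participants, for 5 participants in each of the 16 groups", which gives 40 against 40 for each main effect. The sample size rests on feasibility; no SD, effect size or power is given for MVPA or HEI.

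**The concern.** With two time points, the component-by-time coefficient compares mean changes between factor levels. The component main effect spends a parameter on a baseline difference whose true value is zero, because assignment comes later. A change score subtracts the whole baseline difference; a baseline-adjusted analysis subtracts only the part that predicts the 3-month value. When that part is smaller, chance baseline imbalance adds noise to the estimate.

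The listed covariates do not help if they enter in the natural way, as main effects constant over time. They then shift a person's level at both visits and cancel from the change. The plan says only that it adjusts for them, so this reading is likely but not certain.

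At stake is the precision of the main-effect estimates on MVPA and HEI. These are a listed secondary objective in a small trial whose design is justified by efficient use of the sample.

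**Working it through.** The plan states no precision or power for these outcomes, so there is no figure of its own to reproduce.

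**Inputs from the documents:** 80 evaluable, 40 against 40 per factor; two time points; randomisation after baseline; retention of 70% (null) to 90% (alternative).

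**Assumptions:** r, the baseline-to-3-month correlation, shown for 0.3–0.7; and k, the baseline SD divided by the 3-month SD, first set to 1.

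**Step 1: the tested term is a change score.** The planned model was fitted by maximum likelihood to one simulated complete data set with a time-constant covariate included. The component-by-time coefficient was −0.0936, equal to the raw difference in mean change. With complete, balanced data and these mean terms, the choice of covariance structure does not alter that estimate.

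**Step 2: variances, complete data, k = 1, outcome SD = 1.**

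- Planned: 2 × 2(1−r)/40 = 0.10(1−r).
- Baseline-adjusted: 2 × (1−r²)/40 = 0.05(1−r²).
- Ratio, adjusted to planned: (1+r)/2. Loss in inverse variance: (1−r)/2. Loss on the SE scale: 1 − √((1+r)/2).

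**Step 3: incomplete 3-month data.** With a share q retained, the loss is 1 − (1+r)/[(1+r) + q(1−r)].

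| r | Planned variance | Adjusted variance | Loss, complete | SE scale | Loss, q = 0.9 | Loss, q = 0.7 |
|---|---|---|---|---|---|---|
| 0.3 | 0.070 | 0.0455 | 35% | 19% | 33% | 27% |
| 0.5 | 0.050 | 0.0375 | 25% | 13% | 23% | 19% |
| 0.7 | 0.030 | 0.0255 | 15% | 8% | 14% | 11% |

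At r = 0.8 and 0.9 the complete-data loss is 10% and 5%. The ratios do not depend on N in large samples, so the synopsis figure of 72 participants would not change them. Simulating 4,000 trials of the 2⁴ design with N = 80 gave slightly smaller losses: 34%, 23% and 12% with complete data, and about 8–30% across 70–90% retention.

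**Step 4: unequal variances, complete data.** The ratio becomes (1−r²)/(1 + k² − 2rk).

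- k = 0.8: losses of 22%, 11% and 2% at r = 0.3, 0.5 and 0.7.
- k = 0.7: at r = 0.3, 0.91/1.07 = 0.85, a loss of 15%; at r = 0.5, 0.75/0.79 = 0.95, a loss of 5%; at r = 0.7, 0.51/0.51 = 1, no loss.
- k above 1 makes the loss larger than in Step 2.

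**Step 5: illustration only.** For an assumed main effect of 0.5 SD, two-sided alpha 0.05, k = 1 and complete data, power for planned against adjusted is 47% v 65%, 61% v 73% and 82% v 88% at r = 0.3, 0.5 and 0.7. The chance baseline difference between two levels has SD √(2/40) = 0.22 outcome SDs. At r = 0.5, an imbalance of that size moves the change-score estimate by (1−0.5) × 0.22 = 0.11 SD.

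**The case against.** The planned model is conventional and valid. Under randomisation its contrast is unbiased, and its standard error already allows for chance baseline imbalance. Baseline values are not thrown away: they enter the likelihood as responses, just not as covariates.

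The size of the loss is also open. It depends on r, on k and on retention, and the documents give neither r nor any SD. Eligibility selects people below activity and fruit-and-vegetable guidelines, which could narrow the baseline spread and push k below 1, where the loss shrinks. The screen is self-reported, so how far is unknown.

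These are secondary outcomes of a pilot sized for feasibility, and Strengths and Limitations already warns that its effect sizes may be inconclusive. ANCOVA has its own drawback: without imputation it drops people with no 3-month value, whom the planned likelihood model keeps.

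All of this stands. It limits the size and importance of the point but does not remove it, because in large samples the planned contrast is never more efficient than baseline adjustment. A 6-week measurement, if the synopsis were right about it, would still leave the levels free to differ at baseline.

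**Conclusion.** The plan uses an unbiased but generally less precise estimator than its own data allow. Under k = 1 and complete data the loss is 15–35% of inverse-variance precision for r between 0.7 and 0.3, or about 8–19% on the SE scale. At 70–90% retention it is about 11–33%. It can be near zero when r is high or k is clearly below 1.

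A reader might infer three stronger things that the documents do not support:

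- That the trial will in fact lose 15–35% of its precision. That range needs assumed values of r and k and complete data.
- That the component effects are biased. Averaged over randomisations they are not.
- That the planned estimator is noisier than ignoring baseline whenever r is below 0.5. The threshold is r = k/2, so 0.35 at k = 0.7.

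Any power figure is illustrative, since no target effect is stated. The primary feasibility tests are unaffected. The change is still worth making because it is nearly free.

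**What to change.** Amend Statistical Analysis in Section 4 and the synopsis row for MVPA, HEI and the other outcomes measured at baseline and 3 months.

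- **Preferred:** a constrained longitudinal model with time and component-by-time terms for all four components together, a common baseline mean (no component main effects at baseline), and an unstructured covariance fixed in advance. The covariance must be pre-specified because, once the baseline means are constrained, it determines how much of a baseline imbalance is adjusted for. This model keeps participants who lack a 3-month value.
- **Alternative:** ANCOVA of the 3-month value on its own baseline value plus all four components, with multiple imputation as foreseen under Handling Missing Data. Without imputation, people with no 3-month value drop out.
- If age, cancer type and time since diagnosis stay in a repeated-measures model, let them interact with time so that they can act on the change.

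The cost is analysis wording and about one degree of freedom for the baseline term; covariate-by-time terms would use a few more, depending on how cancer type is grouped. No new data are needed.

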## **Handling Missing Data**

While every effort will be made to avoid missing data, we expect some attrition. If the combined missingness on predictor variables is <5%, missing data will not be replaced. If levels of missing data are higher, we will examine the nature of the missing data and extent of bias it may introduce. We will compare respondents to non-respondents to see if they differ on non-response systematically and assess if missing data are missing completely at random (MCAR), missing at random (MAR), or missing not at random (MNAR). Assuming the data are (MCAR/MAR), multiple imputation methods will be used.

## **Strengths and Limitations.**

One of the biggest limitations of this study is the sample size. The use of a factorial design makes efficient use of the sample, but effect sizes may not provide conclusive evidence for efficacy to make determinations about component inclusion in future trials. However, it makes efficient use of resources and will provide valuable information about feasibility, acceptability, and implementation of intervention components, regardless of effect size. Another limitation is that since the PA intervention is being included as a core component, it will not be possible to disentangle the main effects for this component alone. This randomized factorial pilot trial is testing an innovative theory and evidence-based approach to promoting guideline concordant PA and nutrition in AYAs followed by 3 months of behavioral maintenance. A strength of the intervention is utilizing an existing intervention framework that has been shown to improve PA in this population. The factorial design allows for the simultaneous testing of multiple novel intervention components to examine their feasibility and acceptability while conserving resources. Intervention components will be developed around ACS guidelines for cancer prevention and cancer survivors, which has not been examined in this population. The goal of the intervention is to improve PA and nutrition behaviors among AYAs, which will be beneficial to all survivors, but may provide additional benefits for those that are least compliant and at highest risk for future morbidity and mortality. This is the first intervention design for AYAs to target determinants for frailty and could provide important information for future optimization trials and fully powered RCTs. Information from this pilot will inform future trials to optimize timing, delivery, and dose of promising intervention components. This study will add to the field of cancer prevention and control by testing interventions targeting PA and nutrition behaviors with the goal of meeting guideline recommendations among AYAs to improve survivorship outcomes and reduce health disparities.

## **5. SAFETY MANAGEMENT**

Data safety management in this trial is intended to achieve 4 objectives: 1) to minimize the occurrence of adverse effects, especially those related to the intervention; 2) to effectively manage adverse events as they relate to the study; 3) to identify when the interventions should be suspended because of concerns for participant safety; and 4) to determine when interventions may be resumed after having been suspended. The Principal Investigator ([name]) will have primary responsibility for the safety of participants as it relates to the study protocol, which must be approved by the UNC IRB prior to study initiation. In addition, the North Carolina Translational and Clinical Sciences (TraCS) Institute Data Safety Monitoring Board (DSMB) is responsible for reviewing data from clinical trials approved by the UNC Biomedical IRB. Because the risks to subjects participating in this phase of this study are expected to be low, we do not anticipate the need for a formal Data Safety Monitoring Board. The research team will provide continuous monitoring of participant safety and periodic reporting to the IRB as required, including any Unanticipated Problems/Severe Adverse Events that may have occurred during the study. If risk or complexity is significant, the UNC Office of Human Research Ethics may require additional reporting or alternative data and safety monitoring. Data safety and monitoring activities continue until all participants have completed treatment and until all participants have been followed to the point at which study related adverse events would likely no longer be encountered.

## Participant Safety

The risks to human subjects in this study, including psychological and physical risks, are judged to be minimal. The anticipated benefits are great, insofar as the results will be used to determine if mobile-delivered behavior change strategies are effective for obesity risk reduction in a sample of young adults.

**Psychological Risks:** We expect risk of harm, including psychosocial and emotional distress or breach of confidentiality, as a result of this study to be rare or infrequent. Most communication during the intervention period will take place via telephone, videochat, website, direct emails, or text messages—to deliver intervention components, conduct assessments, or remind participants to complete questionnaires. Mailing of materials to participants will be done with plain packaging. We do not anticipate any risks of harm as a result of these communications. As part of the intervention, participants may be asked about personal factors related to their PA, dietary behaviors, and weight. Participants are not required to share this information and can elect not to share sensitive and confidential information with the study. Intervention content teaches participants about the benefits of daily self-weighing for weight management, addressing certain myths regarding daily self-weighing, and emphasizing the use of the smart scale as a tool or indicator of progress with diet and PA behaviors. Participants will be encouraged to contact the Principal Investigator if they feel they have incurred any emotional distress as a result of study participation. As this is a voluntary study, a participant is free to exit at any point if discomfort should occur.

Participants with emotional concerns will be referred to survivor-specific support resources, including referral to: the UNC Comprehensive Cancer Support Program for psychological counseling; **LIVESTRONG** Navigation, which offers free, confidential, cancer navigation services to support individuals' cancer journey; and CancerCare Counseling, through which oncology social workers offer telephone counseling to help cancer survivors cope with emotional and practical challenges of cancer.

We will collect information at each assessment timepoint on hospitalizations for any psychiatric problem, including depression and eating disorders and make referrals as needed or suspend intervention if symptoms emerge that are study related or if the severity of the psychological symptoms warrant suspension or withdrawal.

**Physical Risks:** There are no major physical risks associated with the PA or healthy eating interventions or data collection. There may be some risk to increasing physical activity, including, but not limited to, injuries to the muscles, ligaments, tendons, and joints of the body. Other risks include abnormal blood pressure, fainting, dizziness, disorders of heart rhythm, exacerbation of exercise-induced asthma symptoms, and very rare instances of heart attack, stroke, or even death. A consensus statement from the American College of Sports Medicine Roundtable on Exercise Guidelines for Cancer Survivors concluded that exercise training is safe after cancer treatments. Although increasing PA can have great benefits, participants may also experience some general fatigue and sore muscles or joints from exercising. Because several studies indicate that walking is the preferred exercise type for an estimated 55%-81% of survivors of varying cancer types, the study focuses on encouraging moderate-intensity walking. To help ensure safety, the study will follow guidelines and safety recommendations for PA set forth by the American College of Sports Medicine. PhD trained staff interventionists will oversee safety of exercise progression and suitability. Materials provided during the course of the intervention will educate participants on exercise safety and inform them of precautions to take when starting an exercise program and how to manage increasing amounts of exercise. Messages will encourage participants to start at a reasonable frequency and intensity of exercise based on their current level and to increase their exercise gradually. The informed consent will also clearly communicate the potential physical risks related to starting an exercise program and increasing PA. Participation is fully voluntary, and we will ask participants to report any problems to the study researchers.

**Unsafe Rate of Weight Loss:** Participants will not receive an intervention designed to produce weight loss, however, making dietary changes and increasing PA can produce a gradual, modest rate of weight loss. The intervention focuses on making small daily changes to their eating in service of shaping dietary quality over

time. Thus, although unlikely, it is still possible that some participants could experience excessive weight loss at a rate that is unsafe. We will carefully monitor rate of weight loss over the course of the study, and take appropriate action as detailed below to ensure participant safety.

Risk of wearable devices. There is also the possibility of minor skin irritation associated with wearable activity tracker devices.

Risk to privacy and/or confidentiality. We expect a breach of confidentiality to be rare or infrequent. Most communication during the study period will take place via telephone, direct emails, text messages, or through the smartphone app—either to deliver questions, conduct assessments, or remind participants to complete questionnaires. We do not anticipate any risks of harm as a result of these communications; however, there is always a possibility that their scale data, tracker data, or activity in the app will be intercepted.

